13.2 Sample Size and Statistical Power

As per CCTN's recommendation for CTN-0053 to closely mimic the adolescent study, we conducted the sample size calculation using the approach described below. Please note that the adolescent study numbering for weeks began with randomization at week 0, and subsequent weekly observations during treatment at weeks 1-8 (8-week trial). However, in contrast, the current study begins with randomization at week 1, and subsequent weekly observations during treatment at weeks 2-13 (12-week trial). As such, for example, week 1 in the adolescent study corresponds to week 2 in the current study.

Sample Size Calculation Approach:

[figure not shown]
1. Obtain the proportions of negative UDS in each week in the Placebo + CM arm from the adolescent study. Only 52/105 participants with positive baseline UDS in the Placebo + CM were used and missing UDS were not imputed while calculating these proportions.

Week	1	2	3	4	5	6	7	8
Proportion	.20	.33	.40	.41	.40	.37	.36	.50

2. The following missing data patterns were observed in the 105 participants from the adolescent study. Here 0 represents missing UDS and 1 represents UDS present. For example, 00000000 denotes that all 8 UDS are missing.

UDS	Pattern	Frequency	Percent
All Missing	00000000	26	25%
	10000000	4	11%
	11000000	2	
(I)	11100000	1	
tone	11111000	2	
anol Ssir	11111100	1	
Monotone Missing	11111110	2	
	00100000	1	20% of participants had
 	01011111	1	23% of UDS missing intermittently
Intermittent Missing	01100000	1	
Mis	01110100	1	
ŧ	01110111	1	
itte	10111111	2	
Ē	11011111	3	
ıteı	11110111	3	
 	11111011	6	
	11111101	2	
All Observed	11111111	46	44%
Total		===	
		105	

- **3.** Assume two different odds ratios (OR = 2.25 and 2) as effect size measures. We assumed auto-regressive (AR(1)) correlations of 0.75 for the within-participant correlation in weekly scores over time, and a baseline tobacco smoking rate of 57% obtained from the adolescent study.
- **4.** Impose fixed site effect (6 sites) that would change the proportion of negative UDS in each of the sites. This will induce the site variability. Below are the proportions of negative UDS in the two arms with treatment effect, OR = 2.25. Similar plots can be obtained for OR = 2, as well as 4 and 5 sites.

- **5.** Simulate the data assuming the proportions from Step 4 and that abstinence rates in weeks 10-13 are the same as weeks 6-9.
- **6.** Impose the missing UDS pattern (from Step 2) to the simulated data. Here we assumed that the missing percentage and missing pattern in weeks 2-13 are similar to weeks 2-9 (obtained from adolescent study and shown in Step 2).

- 7. Impute the missing UDS to be positive in the simulated data.
- **8.** Test the effect of the treatment, NAC + CM compared to Placebo + CM, in weeks 2 through 13. Analyze the simulated data using a GEE (generalized estimating equation) model incorporating overall main treatment effect, week effect, site effects and week-by-treatment interaction effect and baseline tobacco smoking effect.

Following are the sample sizes versus power for the primary outcome measure over 12 weeks (weeks 2-13), at 5% level of significance, under various combinations of assumptions about the main effects of treatment (OR) and the number of sites.

Overall Sample		Pov	wer
Size	Number of Sites	OR = 2.25	OR = 2
300	6	.93	.84
300	5	.94	.86
304	4	.94	.86
252	6	.88	.77
250	5	.89	.79
256	4	.90	.80

In order to ensure sufficient power for the analysis replicating the adolescent study, additional power simulations were conducted for the odds of a cannabinoid-negative weekly urine drug screen over the first 8 weeks of active treatment (weeks 2-9). These power analyses follow exactly as the approach outlined above, but no data was generated for weeks 10-13.

Below are the sample sizes versus power with a 5% level of significance:

Overall Sample		Po	wer
Size	Number of Sites	OR = 2.25	OR = 2
300	6	.88	.78
300	5	.90	.80
304	4	.90	.80
252	6	.83	.71
250	5	.84	.72
256	4	.85	.73

From both tables above, a sample size of 300 provides sufficient power (>79%) to detect the treatment difference corresponding to effect size, odds ratio = 2 with 6 sites, for both the 12-week (weeks 2-13) and 8-week (weeks 2-9) analyses. While a sample size of 252 would be sufficient to detect an OR of 2 for the primary outcome analysis, it does not allow for sufficient power in replicating the adolescent which is a vital component of the proposed study.

Power and Sample Size for End-of-Treatment Abstinence

As per the CCTN's recommendation, we also looked at the power to detect similar effects based on a complete abstinence outcome using UDS over the last 4 weeks of treatment (weeks 10-13). From the adolescent study, 15% of the participants were completely abstinent in the weeks 5-8 in the Placebo + CM arm. All missing urine drug screens were imputed as positive while calculating this proportion. It was assumed that the odds of four cannabinoid-negative urine drug screens in weeks 10-13 was the same as that observed in week 5-8 in the adolescent study.

The simulation study generated data for the Placebo + CM arm using parameter estimates from a logistic regression analysis of the adolescent study, and then the rate in the NAC + CM arm was calculated based on the assumed OR (2.6, 2.5, 2.25 and 2.0) as an effect size measure. The OR of 2.6 is the value estimated from the adolescent study using only those with a positive baseline UDS. From the adolescent study, we assumed 57% of participants would be self-reported tobacco smokers at baseline. To adjust for site heterogeneity, we implemented an approach similar to the sample size calculations for the primary outcome described above. For the set of simulations where there are six sites, site 1 has a 10% increase in odds of end of treatment abstinence, site 2 a 5% increase, site 3 a 10% decrease and site 4 a 5% decrease, and sites 5 and 6 have an 8% and 7% increase and decrease, respectively. The simulations for 4 and 5 sites are set up in a similar fashion. Once the data have been generated, they are analyzed using a logistic regression model with the following covariates: indicator of randomization to NAC + CM, tobacco smoking status and indicators of site. All simulations assume an equal number of participants enrolled per site.

Following are the sample size versus power, at 5% level of significance, for four different odds ratios (ORs). We have also included the estimate from the adolescent study (OR=2.6).

Overall Sample	Number of	Power			
Size	Sites	OR = 2.6	OR = 2.5	OR = 2.25	OR = 2.0
304	4	.93	.91	.82	.68
300	5	.94	.91	.82	.68
300	6	.93	.91	.81	.68
256	4	.89	.86	.76	.61
250	5	.88	.85	.75	.60
252	6	.88	.86	.76	.60

For all three numbers of sites, the power to detect a difference for this outcome measure is <80% for an odds ratio of 2, but there will be sufficient power with approximately 300 participants to detect an OR of 2.25 for 4, 5 and 6 sites, which is deemed a clinically significant effect size.

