9.4 Randomization

Following completion of screening/baseline assessments and determination of study eligibility, participants who return for the randomization visit and continue to be eligible will be randomly assigned to one of the two conditions (NAC or PBO) for 12 weeks of treatment. Random assignment will be on a 1:1 ratio to one of the two conditions. Randomization will be stratified by study site and self-reported tobacco smoking status. The randomization procedure will be conducted centrally through the CTN Data and Statistics Center (DSC), and randomization assignments will not be conveyed to staff or participants. The DSC statistician will generate the randomization schedule using balanced blocks of varying sizes within strata to ensure lack of predictability along with relative equality of assignment across treatment groups. The DSC statistician will review randomization data on a regular basis to ensure that the scheme is being implemented according to plan. A randomization slot, once used, will not be re-allocated.

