13.2.1 Projected Number of Sites

We anticipate that six sites will be used in this study.

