13.4 Significance Testing

The primary outcome will be evaluated using a two-sided test with a type I error rate of 5%. There are several secondary outcomes; however, multiple comparisons will not be adjusted for since these are not part of the study's primary objective.

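### Section 13.2 claims more than 79% power at N=300 with six sites for both analyses, but its 8-week table gives 78%; it also calls N=252 sufficient where its 12-week table gives 77%

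*Protocol*

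**What the plan says.** Protocol Section 13.2 derives power by simulation for the 12-week primary analysis (weeks 2-13) and, separately, for the 8-week analysis meant to replicate the adolescent trial (weeks 2-9). Each has a table by sample size, number of sites and odds ratio. The text below the tables draws two conclusions:

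- From both tables, "a sample size of 300 provides sufficient power (>79%) to detect the treatment difference corresponding to effect size, odds ratio = 2". The same sentence limits this to six sites and applies it to both the 12-week and the 8-week analysis.
- "While a sample size of 252 would be sufficient to detect an OR of 2 for the primary outcome analysis", the smaller sample is rejected because it leaves too little power for the replication analysis, which the protocol regards as vital.

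Section 13.2.1 confirms the number of sites: "We anticipate that six sites will be used in this study".

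**The concern.** The first sentence fixes the sample size, the odds ratio, the number of sites and both analyses, so it points to exactly one cell in each table. One of those two cells does not show what the sentence says.

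The second sentence applies a looser standard than the first. Having just marked sufficiency at more than 79%, it accepts a tabulated .77 as sufficient.

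Together these sentences are the protocol's stated reason for choosing 300 over 252: the smaller sample serves the primary outcome but not replication, and the larger serves both. At six sites and an odds ratio of 2, the tables support neither claim about sufficiency. The text is also a natural reference point if the interim check of sample-size adequacy in Section 13.5 is carried out, so it should state the planned power correctly.

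**Working it through.** **Inputs, all from the protocol.** Two-sided 5% test (Section 13.4: "The primary outcome will be evaluated using a two-sided test with a type I error rate of 5"%); 1:1 allocation (Section 9.4); six sites (Section 13.2.1); odds ratios of 2.25 and 2 (Section 13.2, Step 3); and the two power tables in Section 13.2.

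**Step 1. Read the tables at an odds ratio of 2.**

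| N | Sites | 12-week power | 8-week power |
|---|---|---|---|
| 300 | 6 | .84 | **.78** |
| 300 | 5 | .86 | .80 |
| 304 | 4 | .86 | .80 |
| 252 | 6 | **.77** | .71 |
| 250 | 5 | .79 | .72 |
| 256 | 4 | .80 | .73 |

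The claim for N=300 with six sites is met at 12 weeks (.84) and not at 8 weeks (.78). A figure printed as .78 lies between .775 and .785, so it cannot exceed .79. The claim for N=252 refers to a sample size that occurs only with six sites, where 12-week power is .77. The neighbouring .79 and .80 belong to N=250 with five sites and N=256 with four.

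**Step 2. Are the tables coherent with each other?** Under a normal approximation, z(power) + 1.96 is proportional to the square root of N. Scaling from N=300 to N=252 multiplies it by √(252/300) = 0.9165.

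- 12-week: z(.84) + 1.96 = 0.994 + 1.960 = 2.954. Then 2.954 × 0.9165 − 1.960 = 0.748, giving power .773 (table: .77).
- 8-week: z(.78) + 1.96 = 0.772 + 1.960 = 2.732. Then 2.732 × 0.9165 − 1.960 = 0.544, giving power .707 (table: .71).

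The six-site cells agree across sample sizes, so a misprint of .78 or .77 is unlikely.

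**Step 3. How far short?** By the same scaling, the N needed is N₀ × [(z(target) + 1.96) / (z(tabulated) + 1.96)]².

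- 8-week, from .78 at N=300: for 79%, 300 × (2.766/2.732)² ≈ 308; for 80%, 300 × (2.802/2.732)² ≈ 316.
- 12-week, from .77 at N=252: for 79%, 252 × (2.766/2.699)² ≈ 265; for 80%, 252 × (2.802/2.699)² ≈ 272.

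**Step 4. Simulation, as background only.** Steps 1-8 of Section 13.2 were simulated with the listed placebo rates and missing-data patterns, missing tests set to positive, and a GEE testing the week-averaged treatment effect. Three things had to be assumed. The primary-outcome site effects are in a figure not available here, so the site effects given for end-of-treatment abstinence were used. The generator of correlated binary data and the extension of the missing patterns to 12 weeks are not specified.

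A Markov generator with correlation 0.75 (1,500 runs per cell, Monte Carlo standard error about 1 point) gave these values at an odds ratio of 2:

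| N | Analysis | Simulated | Table |
|---|---|---|---|
| 300 | 8-week | .758 | .78 |
| 252 | 8-week | .724 | .71 |
| 300 | 12-week | .809 to .844 | .84 |
| 252 | 12-week | .753 to .781 | .77 |

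The 12-week ranges cover two ways of extending the missing patterns. A Gaussian copula with latent correlation 0.75 gave about .84 to .85 for the 8-week cell at N=300. That spread is wider than the discrepancy at issue, so simulation cannot settle which figure is right. The finding rests on Step 1.

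**The case against.** The best case on the other side is about weight. The 8-week shortfall is between one and two points, it concerns a secondary analysis, and it arises at the smaller of the two assumed odds ratios; at 2.25 the same cell is .88. Primary power at N=300 is .84 and is unaffected. The correct figures are printed just above the sentence. The decision also survives: if 252 gives .77 and .71, it is weaker on both analyses and the case for 300 is stronger. All of that stands and limits the seriousness of the point.

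It can also be argued that calling 252 sufficient involves no number, and that the protocol sets no formal cut-off for this outcome. That is partly fair: this limb is an inconsistency of standard, whereas the first is a false statement. But the only mark of sufficiency in that paragraph is the more-than-79% figure. In the end-of-treatment part of Section 13.2 the protocol itself sets power below 80% against sufficient power. A tabulated .77 fails both.

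It is also right that this is a mismatch between text and table rather than a miscalculation, and that simulated values should not be used to decide it. Neither point touches the table read-off.

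**Conclusion.** The concern holds. The statement that N=300 with six sites gives more than 79% power in both analyses at an odds ratio of 2 is wrong for the 8-week analysis, where the protocol's own table gives 78%. The description of N=252 as sufficient for the primary outcome conflicts with the tabulated 77% and the standard used one sentence before.

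The size is small: one to two points against the stated mark in each case. By normal-approximation scaling, that corresponds to about 8 participants for the 8-week analysis (308 against 300) and about 13 for the 12-week analysis (265 against 252). The conclusion assumes only that the printed tables are the protocol's actual results, which their agreement across sample sizes supports. The sample size of 300 and the primary analysis are not called into question.

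**What to change.** Replace the two sentences below the tables in Section 13.2 with the tabulated values, for example: With 300 participants at six sites, power to detect an odds ratio of 2 is 84% for the 12-week analysis and 78% for the 8-week analysis; with 252 participants it is 77% and 71%, below 80% for both. Keep N=300.

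If the sponsor believes the text reflects the intended simulation and the tables do not, the tables should be rerun and corrected instead, so that text and tables agree.

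The cost is two sentences and a slightly less favourable stated power for the replication analysis. Recruitment, procedures and analyses do not change.

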13.2.1 Projected Number of Sites

We anticipate that six sites will be used in this study.

13.2.2 Projected Number of Participants per Site

We anticipate that each site will enroll and randomize approximately 50 (between 40-60) participants over the 12-month recruitment period.

13.3 Missing Data and Dropouts

A sensitivity analysis will be performed to determine how the missing data mechanism affects the results. One approach that will be used within the sensitivity analysis is to impute missing urine test results based on completed tests just before and after the missing test, which is common in substance use research.

13.4 Significance Testing

The primary outcome will be evaluated using a two-sided test with a type I error rate of 5%. There are several secondary outcomes; however, multiple comparisons will not be adjusted for since these are not part of the study's primary objective.

13.5 Interim Analyses

In coordination with the centralized Data and Statistics Center, a DSMB will monitor the progress of the trial. If recruitment progresses slowly enough to allow interim analysis to impact a substantial proportion of future recruitments, then interim analysis will be conducted. One interim check would focus on the nuisance parameters for the primary abstinence outcome measure in order to assess the adequacy of the projected study sample size. This check would not reveal the treatment effect observed in the trial at the time of this interim analysis. The parameters to be considered could include the missingness pattern and the within-participant correlation in consecutive weekly urine drug screens. If either is substantially different from the assumed values, there may be a need to adjust the sample size. This analysis would be conducted when approximately half of the participants (*n*=150) have been enrolled and have completed the active treatment phase of the study. The results of this analysis would be presented to the DSMB, who will then provide a recommendation to the NIDA CCTN regarding whether the target sample size should be modified. A decision regarding any such modification would be made subsequently by the CCTN, taking into consideration the recommendation of the DSMB.

In addition, formal statistical interim analyses for efficacy and futility may be performed. For an interim efficacy analysis we would use two-sided, symmetric O'Brien-Fleming type boundaries (O'Brien & Fleming, 1979) generated using the flexible Lan-DeMets approach to group sequential testing (Lan & DeMets, 1983). The monitoring guidance for early stopping in a futility analysis would be based upon an approach of conditional power (Jennison & Turnbull, 2000). In addition, safety interim looks will be performed (without formal statistical testing) at the regular DSMB meetings or unscheduled times per the DSMB's request.

13.6 Types of Analyses

All analyses will follow the intent-to-treat principle, where all subjects are analyzed and the covariate of interest is the treatment assignment, not the treatment received. Analysis of the safety population can be performed upon request. Further analyses may consider the amount of NAC received based on treatment compliance, or the amount of incentives earned.

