A post hoc sensitivity analysis was performed on odds of negative urine cannabinoid tests during treatment, using multiple methods to manage missing data and participant dropouts. In addition to the ITT approach noted above (n=116), a modified ITT analysis that examined participants who received at least one dose of study medication (n=106) and a per-protocol analysis using available data (n=varying) were performed. Using a modified ITT analysis, participants in the NAC group had 2.2 times the odds of submitting negative urine cannabinoid tests, compared to those in the placebo group (OR=2.2 [95% CI: 1.1-4.5], p=0.04) during the treatment phase of the study. When only examining available data (per-protocol analysis), participants in the NAC group had 2.4 times the odds of submitting negative urine cannabinoid tests than those in the placebo group (OR=2.4 [95% CI: 1.1-4.5], p=0.04). Finally, combinatorial graphical methods for assessing the impact of missing data on significance of findings were also employed, in which every permutation of missing data assignment was considered, and a subsequent logistic regression performed (Hollis, 2002). For the majority of missing data assignments that could be reasonably expected, the odds ratio was still significant. In general, the selection of missing data handling had little effect on analytic outcomes.

Additional secondary analyses were conducted to explore end-of-treatment outcomes, using a sample restricted to participants with positive urine cannabinoid tests at baseline (*n*=105). While the study was not powered for these outcomes, it was felt that these were particularly relevant to evaluate meaningful clinical impact of the intervention. Criteria for four-week end-of-treatment abstinence were as follows:

For urine cannabinoid test, binary outcome defined as:

- 1 if the participant submitted a negative urine cannabinoid test in each of the last four weeks of the active treatment period
- 0 otherwise (including those who dropped out prior to the last four weeks)

For self-report, binary outcome defined as:

- 1 if the participant reported no marijuana use on each of the last 28 days (four weeks) of the active treatment period
- 0 otherwise

Table 1. Four-week end-of-treatment abstinence outcomes.

Method of Handling	Data	Proportion Abstinent	OB (n value)	
Missing Data	Data	Placebo	NAC	OR (p -value)
Missing on Positive	UDS	8/52=0.15	17/53=0.32	2.59 (0.045)

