13.9 Safety Analysis

Adverse events (AEs), including serious adverse events (SAEs), will be summarized by system organ class and preferred term using MedDRATM (The Medical Dictionary for Regulatory Activities). Adverse events will be presented in two ways: (1) the number and proportion of participants experiencing at least one incidence of each event will be presented overall and by treatment group; and (2) a table displaying the total number of each event will be given overall and by treatment group. Listings of serious adverse events will be given, sorted by treatment, system organ class, and preferred term. Detail in these listings will include severity, relationship to study drug, and action taken as available. Treatment arm differences will be monitored by the DSMB.

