Pregnancy: All pregnancies that occur on study will be captured on a pregnancy CRF and not separately reported as an AE or a serious event. Women who become pregnant during the study period will be discontinued from further study drug/intervention referred for medical care, and the pregnancy followed until an outcome is known. Women who terminate the pregnancy

may be reinitiated on study medication based on the judgment of the medical clinician. Women who become pregnant will be eligible to continue study assessments.

Medical History: A thorough medical history during the eligibility assessment phase should record any chronic, acute, or intermittent preexisting or current illnesses, diseases, or symptoms of the participant, to avoid reporting pre-existing conditions as new AEs and to assist in the assessment of worsening in intensity or severity of these conditions that would indicate an AE. Stable chronic conditions, such as arthritis, which are present prior to clinical trial entry and do not worsen are not considered AEs.

Site's Role in Eliciting and Reporting Adverse Events: Appropriately qualified and trained research personnel will elicit participant reporting of AEs and SAEs at each study visit designated to collect AEs. Adverse events (medical and/or psychiatric) assessment will initiate with participant consent and follow-up will continue through 30 days post last study visit. Research personnel will obtain as much information as possible about the reportable AE/SAE to complete the AE/SAE forms and will consult as warranted.

Standard reporting, within 7 days of the site becoming aware of the event, is required for reportable AEs. Expedited reporting (within 24 hours of their occurrence and/or site's knowledge of the event) is required for reportable SAEs (including death and life-threatening events). Local site staff is responsible for reporting serious events to their IRB, per their IRB's guidelines.

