19.2 Oversight of Clinical Responsibilities

A. Site Principal Investigator

Each participating site's PI is responsible for study oversight, including ensuring human research subject protection by designating appropriately qualified, trained research staff and medical clinicians to assess, report, and monitor adverse events.

Regarding safety and in accordance with FDA reporting requirements, all Adverse Events (AEs) occurring during the course of the clinical trial will be collected, documented, and reported by the investigator or sub-investigators according to the Protocol. The assessment of Adverse Events (medical and/or psychiatric) will commence at the time of participant consent and will continue through 30 days post last active treatment visit.

The occurrence of AEs and Serious Adverse Events (SAEs) will be assessed at each clinic visit during the study. Serious adverse events will be followed until resolved or considered stable, with reporting to the CCC Safety Monitor/Medical Monitor through the follow-up period.

Standard reporting, within 7 days of the site becoming aware of the event, is required for reportable AEs. Expedited reporting (within 24 hours of their occurrence and/or site's knowledge of the event) is required for reportable SAEs (including death and life-threatening events).

B. Medical Monitor/Safety Monitor

The NIDA Clinical Coordinating Center (CCC) Safety Monitor/Medical Monitor is responsible for reviewing all adverse events and serious adverse events reported. All SAEs will be reviewed at the time they are reported in the EDC. The Medical Monitor will also indicate concurrence or not with the details of the report provided by the site PI. Where further information is needed the Safety Monitor/Medical Monitor will discuss the event with the site. Reviews of SAEs will be conducted in the AdvantageEDC data system and will be a part of the safety database. All AEs are reviewed on a weekly basis to observe trends or unusual events.

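### As written, the by-arm adverse-event proportions in 13.9 include randomised participants who never took study drug, because 13.6 puts every analysis on intent-to-treat and leaves the safety population optional

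*Protocol*

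**What the plan says.** Protocol section 13.6 sets one principle for the whole trial: "All analyses will follow the intent-to-treat principle, where all subjects are analyzed and the covariate of interest is the treatment assignment, not the treatment received". It then gives safety a single sentence: "Analysis of the safety population can be performed upon request". The protocol does not say who belongs to that population.

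Section 13.9 describes the adverse-event tables. In the first of its two presentations, "the number and proportion of participants experiencing at least one incidence of each event will be presented overall and by treatment group". It names no denominator, does not depart from 13.6, and does not say how events that began before the first dose are handled. It leaves the monitoring of arm differences to the DSMB.

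On collection, Appendix A (18.0) states: "Adverse events (medical and/or psychiatric) assessment will initiate with participant consent and follow-up will continue through 30 days post last study visit". Appendix B (19.2) starts at the same point but ends the window elsewhere; assessment "will commence at the time of participant consent and will continue through 30 days post last active treatment visit".

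Section 13.1 refers further detail on planned analyses and reporting to a statistical analysis plan, which is not at hand.

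**The concern.** Analysing everyone as randomised is cautious for efficacy, because participants who were never exposed pull the arms together. The same pull is not cautious for safety. A participant who took no capsule cannot have an event caused by the capsules, yet adds one to the denominator. Every proportion of drug-caused events falls, and so does the absolute difference between arms.

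These tables are the main by-arm view of tolerability. Under 13.5, interim safety looks involve no formal testing, so what the DSMB sees is the displayed rates and differences.

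Non-dosing is plausible here. Under 9.5.1 participants are given a supply to take home, and no observed first dose is described. The adolescent trial that this study is built to mirror had randomised participants who took no dose (4.2.2).

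A second, smaller question follows from collection starting at consent. If events with onset before first dose enter the arm tables, they add a component that treatment cannot have influenced.

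**Working it through.** **No figure to reproduce.** The protocol states no adverse-event rate and no expected size for the safety population. The arithmetic below is illustrative.

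**Step 1: who is in the denominator.** Section 13.6 covers all analyses and all subjects. Section 13.9 takes no exemption, and the only safety-specific set is optional. Together these give all randomised participants, by assigned arm. This is an inference from 13.6, since 13.9 does not name the denominator.

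**Step 2: share undosed.** The only figures in the document come from the adolescent trial (4.2.2): 116 randomised, and 106 in the modified analysis limited to those with at least one dose.
- u = (116 − 106)/116 = 10/116 = 8.6%
- Applied to the planned 300: 300 × 10/116 = 25.9, about 26 people

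The rate in this adult trial is unknown, so a range is shown.

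**Step 3: effect on the displayed rate.** Let p be the event proportion among dosed participants, and take the undosed to report no events. Then:

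displayed proportion = p × (1 − u)

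With illustrative p of 20% on NAC and 10% on placebo, and equal u in both arms:

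| u | NAC | Placebo | Difference | Ratio |
|---|---|---|---|---|
| 0 (dosed only) | 20.0% | 10.0% | 10.0 points | 2.0 |
| 2% | 19.6% | 9.8% | 9.8 points | 2.0 |
| 5% | 19.0% | 9.5% | 9.5 points | 2.0 |
| 8.6% | 18.3% | 9.1% | 9.1 points | 2.0 |
| 15% | 17.0% | 8.5% | 8.5 points | 2.0 |

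The relative understatement equals u whatever p is. At 8.6%, the dosed-only rate is 1/(1 − 0.086) = 1.094 times the displayed one.

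**Step 4: two conditions.** If non-dosing differs by arm, the ratio moves too. With 12% undosed on NAC and 5% on placebo (illustrative), 0.20 × 0.88 = 17.6% and 0.10 × 0.95 = 9.5%, a ratio of 1.85. If undosed participants do report background events, at the same rate in both arms, the proportions fall less. With equal u the difference still shrinks by the factor 1 − u, and the ratio then moves as well.

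**Step 5: events before first dose.** Let q be the chance of such an event, equal in both arms and independent of later events. A table that includes them shows 1 − (1 − q)(1 − p) in each arm. Both proportions rise, and the difference becomes (1 − q) times its former value. The documents give no q. Section 9.3 allows up to two weeks from consent to complete screening, and 14.4.5 does not require mild unrelated events in the data system. The direction is clear; the size cannot be estimated.

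**The case against.** The strongest reply has four parts. Section 13.9 names no denominator. The reference in 13.6 to a covariate suits modelled comparisons better than descriptive tables. The statistical analysis plan may define a safety set and a treatment-emergent rule. And the consequences are limited, because the tables are descriptive, the serious-event listings carry relationship to study drug, the medical monitor reviews all events weekly (19.2), and a safety-population analysis is available to anyone who asks.

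Much of this stands. The all-randomised denominator is how the text reads, not something 13.9 spells out, and the absence of a treatment-emergent rule from a protocol is not in itself an error. But 13.6 is a stated choice rather than a silence: it says all analyses, and in the next sentence makes the safety population the exception. An analysis plan that used dosed participants by default would contradict it.

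Three stronger readings are tempting and are not supported.

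- **A quarter of the denominator is empty.** Section 13.2 shows 26 of 105 adolescents with every urine test missing. Giving no urine is not the same as taking no drug. At most 10 of those randomised were undosed, so at least 26 − 10 = 16 of the 26 took a dose and would stay in a dosed-only set. That loss is missing follow-up, which a change of population does not cure.
- **Events before first dose dilute drug-related rates.** They cannot be drug-related. They raise all-event rates in both arms and narrow the contrast, which is a different effect.
- **The arm tables will count from consent, at a calculable cost to the risk ratio.** The consent rule in Appendices A and B governs collection, not tabulation. Any ratio would rest on invented rates and would overlook the mild unrelated events that need not enter the database.

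**Conclusion.** The point holds in a limited form. Taken together, 13.6 and 13.9 put never-dosed participants into the by-arm adverse-event proportions and leave the more suitable population undefined and optional.

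If non-dosing resembles the adolescent trial, proportions and absolute arm differences are understated by about 9% in relative terms; a range of 2% to 15% undosed gives an understatement of 2% to 15%. This rests on the adolescent figure carrying over to adults, on the undosed reporting no events, and on illustrative event rates. With equal non-dosing in both arms and no events among the undosed, the risk ratio is unaffected, so the comparison would not be distorted in relative terms.

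The bias is modest, but it is avoidable and favours the appearance of safety, so the change is worth making before the tables are programmed. The handling of events before first dose is secondary: a matter of clear presentation, with no estimable size.

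**What to change.** 1. In 13.6, limit the intent-to-treat sentence to efficacy analyses.
2. In 13.6, define the safety population as all randomised participants who took at least one dose of study drug, state how arm is assigned within it, and delete the sentence that makes it optional.
3. In 13.9, name that population as the default denominator for the adverse-event tables, and keep a listing for all randomised participants so that no event is lost from view.
4. In 13.9, show events with onset before first dose separately from the by-arm tables.
5. In the same edit, reconcile the end of the adverse-event window, which Appendix A counts from the last study visit and Appendix B from the last active treatment visit.

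The cost is a few sentences, with no change to efficacy analysis. Some extra programming is needed to derive first-dose status from the medication logs and weekly pill counts in 9.5.1. The protocol does not expressly list first-dose date or event-onset date as recorded fields, so the case report forms should be checked for both.
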